## **9.2 Adverse Events**

The definitions of an AE or SAE can be found in [Appendix 3](#).

AEs will be reported by the participant (or, when appropriate, by a caregiver, a surrogate, or the participant's LAR).

The investigator and any qualified designees are responsible for detecting, documenting, and reporting events that meet the definition of an AE or SAE and remain responsible for following up

on AEs that are serious, considered related to the study intervention or the study, or that caused the participant to discontinue before completing the study.

Use CTCAE v5 definitions and grading for safety reporting of all AE and SAEs on the case report form.

Immune-mediated adverse events are AEs consistent with an immune-mediated mechanism or immune-mediated component for which non-inflammatory etiologies (eg, infection or tumor progression) have been ruled out. IMAEs can include events with an alternate etiology which were exacerbated by the induction of autoimmunity. Information supporting the assessment will be collected on the participant's case report form.

**Refer to Appendix 3 for SAE reporting.**

#### **9.2.1 Time Period and Frequency for Collecting AE and SAE Information**

Collect all nonserious adverse events (not only those deemed to be treatment related) continuously during the treatment period and for a minimum of 135 days following discontinuation of study treatment. All AEs associated with SARS-CoV-2 infection must be collected from time of consent and during the treatment period. All SAEs must be collected from the time of signing the consent, including those thought to be associated with protocol-specified procedures, and within 135 days following discontinuation of dosing, except in cases where a study participant has started a new anti-neoplastic therapy. However, any SAE occurring after the start of a new treatment that is suspected to be related to study intervention by the investigator will be reported.

For participants randomized to treatment and never treated with study drug, collect SAEs for 30 days from the date of randomization.

All SAEs, and all AEs (SAEs and non-serious AEs) associated with confirmed or suspected SARS-CoV-2 infection must be collected from the date of the participant's written consent until 135 days following discontinuation of dosing. Collect all nonserious adverse events, not only those deemed to be treatment-related, (with the exception of non-serious AEs related to SARS-CoV-2 infection) continuously during the treatment period and for a minimum of 135 days following discontinuation of study treatment.

The investigator must report any SAE that occurs after these time periods and that is believed to be related to study intervention or protocol-specified procedure (eg, a follow-up skin biopsy).

- Medical occurrences that begin before the start of study intervention but after obtaining informed consent will be recorded on the appropriate section of the eCRF module.
- All SAEs will be recorded and reported to Sponsor or designee within 24 hours, as indicated in Appendix 3.
- The investigator will submit any updated SAE data to the sponsor or designee within 24 hours of updated information being available.

Investigators are not obligated to actively seek AEs or SAEs in former study participants. However, if the investigator learns of any SAE, including a death, at any time after a participant

has been discharged from the study, and he/she considers the event reasonably related to the study intervention or study participation, the investigator must promptly notify the Sponsor.

The method of evaluating and assessing causality of AEs and SAEs and the procedures for completing and reporting/transmitting SAE reports are provided in [Appendix 3](#).

### **9.2.2     *Method of Detecting AEs and SAEs***

AEs can be spontaneously reported or elicited during open-ended questioning, examination, or evaluation of a participant. Care should be taken not to introduce bias when collecting AEs and/or SAEs. Inquiry about specific AEs should be guided by clinical judgement in the context of known AEs, when appropriate for the program or protocol.

All nonserious adverse events (not only those deemed to be treatment-related) should be collected continuously during the treatment period and for a minimum of 135 days following discontinuation of study treatment.

Every adverse event must be assessed by the investigator with regard to whether it is considered immune-mediated. For events which are potentially immune-mediated, additional information will be collected on the participant's case report form.

### **9.2.3     *Follow-up of AEs and SAEs***

- Nonserious AEs should be followed to resolution or stabilization, or reported as SAEs if they become serious (see [Appendix 3](#)).
- Follow-up is also required for nonserious AEs that cause interruption or discontinuation of study intervention and for those present at the end of study intervention as appropriate.
- All identified nonserious AEs must be recorded and described on the nonserious AE page of the CRF (paper or electronic). Completion of supplemental CRFs may be requested for AEs and/or laboratory test result abnormalities that are reported/identified during the study.

All SAEs will be followed until resolution, until the condition stabilizes, until the event is otherwise explained, or until the participant is lost to follow-up (as defined in [Section 8.3](#)).

Further information on follow-up procedures is given in [Appendix 3](#).

### **9.2.4     *Regulatory Reporting Requirements for SAEs***

Prompt notification by the investigator to the Sponsor of SAEs is essential so that legal obligations and ethical responsibilities toward the safety of participants and the safety of a product under clinical investigation are met.

An investigator who receives an investigator safety report describing SAEs or other specific safety information (eg, summary or listing of SAEs) from the Sponsor will file it along with the Investigator's Brochure and will notify the IRB/IEC, if appropriate according to local requirements.

The Sponsor or designee must report AEs to regulatory authorities and ethics committees according to local applicable laws and regulations. A SUSAR (suspected, unexpected serious

adverse reaction) is a subset of SAEs and must be reported to the appropriate regulatory authorities and investigators following local and global guidelines and requirements.

### **9.2.5     *Pregnancy***

If, following initiation of the study intervention, it is subsequently discovered that a participant is pregnant or may have been pregnant at the time of study exposure, including during at least 5 months after study product administration, the investigator must immediately notify the BMS Medical Monitor/designee of this event and complete and forward a Pregnancy Surveillance Form to the BMS designee within 24 hours of awareness of the event and in accordance with SAE reporting procedures described in [Appendix 3](#).

Follow-up information regarding the course of the pregnancy, including perinatal and neonatal outcome and, where applicable, offspring information, must be reported on the Pregnancy Surveillance Form. Protocol-required procedures for study discontinuation and follow-up must be performed on the participant.

For WOCBP who are partners of male participants in the study, pregnancy reporting is not required.

### **9.2.6     *Laboratory Test Result Abnormalities***

The following laboratory test result abnormalities should be captured on the nonserious AE CRF page or SAE eCRF, as appropriate. Paper forms are only intended as a back-up option when the electronic system is not functioning.

- Any laboratory test result that is clinically significant or meets the definition of an SAE
- Any laboratory test result abnormality that required the participant to have study intervention discontinued or interrupted
- Any laboratory test result abnormality that required the participant to receive specific corrective therapy

It is expected that, wherever possible, the clinical rather than laboratory term would be used by the reporting investigator (eg, anemia vs low hemoglobin value).

### **9.2.7     *Potential Drug-induced Liver Injury***

Wherever possible, timely confirmation of initial liver-related laboratory abnormalities should occur prior to the reporting of a potential drug-induced liver injury (DILI) event. All occurrences of potential DILIs meeting the defined criteria must be reported as SAEs (see [Section 9.2](#) and [Appendix 3](#) for reporting details).

Potential DILI is defined as:

- Aminotransferase (AT) ALT or AST elevation > 3 times upper limit of normal (ULN)  
AND
- Total bilirubin > 2 times ULN, without initial findings of cholestasis (elevated serum alkaline phosphatase)

AND

- No other immediately apparent possible causes of AT elevation and hyperbilirubinemia, including, but not limited to, viral hepatitis, pre-existing chronic or acute liver disease, or the administration of other drug(s) known to be hepatotoxic.

### **9.2.8      *Other Safety Considerations***

Any significant worsening of conditions noted during interim or final physical examinations, ECG, x-ray filming, or any other potential safety assessment required or not required by the protocol should also be recorded as a nonserious AE or SAE, as appropriate, and reported accordingly.

### **9.3            *Overdose***

An overdose is defined as the accidental or intentional administration of any dose of a product that is considered both excessive and medically important. Overdoses that meet the regulatory definition of SAE will be reported as an SAE (see [Appendix 3](#)).

In the event of an overdose, the investigator should:

- Contact the Medical Monitor/designee immediately
- Closely monitor the participant for AEs/SAEs and laboratory abnormalities
- Document the quantity of the excess dose as well as the duration of the overdosing in the CRF

Decisions regarding dose interruptions or modifications will be made by the investigator in consultation with the Medical Monitor/designee based on the clinical evaluation of the participant and documented.

### **9.4            *Safety***

Planned time points for all safety assessments are listed in the Schedule of Activities.

#### **9.4.1        *Physical Examinations***

Refer to Schedule of Activities, [Section 2](#).

#### **9.4.2        *Vital signs***

Refer to Schedule of Activities, [Section 2](#).

#### **9.4.3        *Electrocardiograms***

Refer to Schedule of Activities, [Section 2](#).

#### **9.4.4        *Clinical Safety Laboratory Assessments***

Investigators must document their review of each laboratory safety report.

All clinical safety laboratory assessments will be performed locally per [Section 2](#) (Schedule of Activities).

**Table 9.4.4-1: Clinical Laboratory Assessments**

Hematology - CBC	
Hemoglobin	
Hematocrit	
Total leukocyte count, including differential	
Platelet count	
Chemistry	
Aspartate aminotransferase (AST)	Albumin - screening only
Alanine aminotransferase (ALT)	Sodium
Total bilirubin	Potassium
Alkaline phosphatase (ALP)	Chloride
Lactate dehydrogenase (LDH)	Calcium
Creatinine	[REDACTED]
Blood urea nitrogen (BUN) or serum urea level	Phosphorus
Glucose	TSH, free (or total) T3 and free (or total) T4 - screening
	TSH, with reflexive f(or t)T3 and f(or t)T4 if TSH is abnormal - on treatment
[REDACTED]	
[REDACTED]	
[REDACTED]	
Serology	
Hepatitis B/C	[REDACTED], (screening only; testing for HIV must be performed at sites where mandated by local requirements [see Appendix 9 ]).
Other Analyses	
Pregnancy test (WOCBP only; minimum sensitivity 25 IU/L or equivalent units of HCG; screening, predose, and, follow-up. During follow-up,	[REDACTED]
Follicle stimulating hormone (FSH) screening - only required to confirm menopause in women < age 55. If FSH does not confirm postmenopausal status, pregnancy testing is required as per SOA.	

Abbreviations: CBC, complete blood count; [REDACTED]; ft3, free T3; ft4, free T4; HBsAG, hepatitis B virus surface antigen; HCG, human chorionic gonadotropin; HCV, hepatitis C virus; HIV, human immunodeficiency virus; [REDACTED] SOA, Schedule of Activities; T3, triiodothyronine; T4, thyroxine; TSH, thyroid stimulating hormone; tT3, total T3; tT4, total T4; WOCBP, women of child bearing potential.

[figure not shown]
[REDACTED] [REDACTED]

[figure not shown]
[REDACTED]

[figure not shown]

[figure not shown]
#### **9.4.6      *Imaging/Other Safety Assessment***

[figure not shown]
Any incidental findings of potential clinical relevance that are not directly associated with the objectives of the protocol should be evaluated and handled by the study investigator as per standard medical/clinical judgment.

[figure not shown]

[figure not shown]

#### **9.8.2.1 *Tumor Sample Collection***

The Investigator, in consultation with the radiology staff, must determine the degree of risk associated with the procedure and find it acceptable. Biopsies may be done with local anesthesia or conscious sedation. Institutional guidelines for the safe performance of biopsies should be followed. Excisional biopsies may be performed to obtain tumor biopsy samples. Invasive procedures that require general anesthesia should not be performed to obtain a biopsy specimen; however, if a surgical procedure is performed for a clinical indication, excess tumor tissue may be used for research purposes with the consent of the participant. Detailed instructions of the obtaining, processing, labeling, handling, storing, and shipping of specimens will be provided in a separate Laboratory Manual.

## **9.9 Additional Research**

This protocol will include residual sample storage for additional research.

### **For All US Sites**

Additional research is required for all study participants, except where prohibited by IRBs/ethics committees, prohibited by local laws or regulations, or academic/institutional requirements. Where one or more of these exceptions occurs, participation in the additional research should be encouraged but will not be a condition of overall study participation.

- If the IRB/ethics committees and site agree to the mandatory additional research retention and/or collection, then the study participant must agree to the mandatory additional research as a requirement for inclusion in the study.
- If optional participation is permitted and approved, then the study participants may opt out of the additional research retention and/or collection.

[figure not shown]
## For non-US Sites

Additional research is optional for all study participants, except where retention and/or collection is prohibited by local laws or regulations, ethics committees, or institutional requirements.

This collection for additional research is intended to expand the translational R&D capability at BMS, and will support as yet undefined research aims that will advance our understanding of disease and options for treatment. It may also be used to support health authority requests for analysis, and advancement of pharmacodiagnostic development to better target drugs to the right patients. This may also include genetic/genomic exploration aimed at exploring disease pathways, progression and response to treatment etc.

## Sample Collection and Storage

All requests for access to samples or data for additional research will be vetted through a diverse committee of the study Sponsor's senior leaders in Research and Development (or designee) to ensure the research supports appropriate and well-defined scientific research activities.

Samples kept for future research will be stored at the BMS Biorepository in [REDACTED] or an independent, BMS-approved storage vendor.

The manager of these samples will ensure they are properly used throughout their usable life and will destroy the samples at the end of the scheduled storage period, [REDACTED] [REDACTED] after the end of the study or the maximum allowed by applicable law.

Transfers of samples by research Sponsor to third parties will be subject to the recipient's agreement to establish similar storage procedures.

Samples will be stored in a coded fashion, and no researcher will have access to the key. The key is securely held by the Investigator at the clinical site, so there is no direct ability for a researcher to connect a sample to a specific individual.

Further details of sample collection and processing will be provided to the site in the procedure manual.

**Table 9.9-1: Residual Sample Retention for Additional Research Schedule**

Sample Type	Time points for which residual samples will be retained
[REDACTED]	All
Other derived/extracted materials from primary collection samples	All

## 9.10 Other Assessments

Not applicable.

[REDACTED]

[REDACTED]

[REDACTED]

[REDACTED]

[REDACTED]

[REDACTED]

[REDACTED]

[REDACTED]

## 10 STATISTICAL CONSIDERATIONS

### 10.1 Statistical Hypotheses

[figure not shown]
The primary hypothesis for the study is that nivo + rela FDC is superior to nivolumab monotherapy in achieving RFS as assessed by the investigator.

The null hypothesis to be tested in relation to the primary endpoint is as follows:

- 1) Nivo + rela FDC is not different from nivolumab monotherapy with respect to RFS per investigator.

The null hypothesis corresponding to the key secondary endpoint is as follows:

- 1) Nivo + rela FDC is not different from nivolumab monotherapy with respect to overall survival.

[figure not shown]

## **10.2 Sample Size Determination**

[figure not shown]
### **10.2.1 *Recurrence-free Survival***

The primary objective of the study is to compare RFS of nivo + rela FDC to nivolumab monotherapy in participants with completely resected Stage IIIA (> 1 mm tumor in lymph node), Stage IIIB/C/D, or Stage IV NED melanoma.

The sample size calculations were simulated using East® and Statistical Analysis System (SAS®) software (SAS Institute, North Carolina, USA).

### 10.3 Analysis Sets

For the purposes of analysis, the following populations are defined:

Population	Description
Enrolled	All participants or their legally acceptable representative who signed an informed consent and were registered into IRT.
Randomized	All participants who were randomized to any treatment arm in the study.
Safety	All participants who take at least 1 dose of double-blind study treatment. Data in this data set will be analyzed based on randomized treatment, except if a participant received the same incorrect treatment throughout the study, then the participant will be analyzed based on the treatment received.
[REDACTED]	[REDACTED]
[REDACTED]	[REDACTED]
[REDACTED]	[REDACTED]

Abbreviations: [REDACTED] IRT, interactive response technology; [REDACTED]

Defined Analysis Data Sets	Description
Analysis set for [REDACTED] of RFS	All randomized participants. Refer to Table 10.4.1-2 for details of intercurrent strategy.
Analysis set for [REDACTED] of DMFS	All randomized Stage III/IVA/IVB participants. Refer to Table 10.4.1-2 for details of intercurrent strategy.
Analysis set for [REDACTED] of OS	All randomized participants. [REDACTED]
Analysis set for safety	All safety events reported for all randomized participants who are exposed to study drug. For participants who discontinue study intervention, all events post-discontinuation up to Day 135 post last dose of study intervention will be included in the safety summaries.

Abbreviations: DMFS, distant metastasis-free survival; OS, overall survival; RFS, recurrence-free survival.

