**Table 2-3: Follow-up Assessments (CA224098)**

Procedure	Follow-Up Visits 1 & 2 a	Long-term Follow-up b	Notes: c
Safety Assessment			
Targeted Physical Examination, Vital Signs, and Performance Status	X		Include weight, blood pressure, heart rate, temperature, performance status.
AE and SAE Assessment	X* (see notes)	X* (see notes)	
Record at each visit. All SAEs and non-serious AEs should be collected continuously during the treatment period and for a minimum of 135 days following discontinuation of study treatment.
 
*Beyond 135 days from the last dose of study therapy, participants will be followed for drug-related AEs/SAEs until resolution, return to baseline, or event(s) is deemed irreversible, or until the participant is lost to follow-up, or withdraws study consent.
 
For all confirmed or suspected SARS-CoV-2 infections, participants will be followed for all SAEs, non-serious AEs of special interest (as defined in Section 9.2.3), and all AEs (SAEs and non-serious AEs) until resolution, the condition stabilizes, the event is otherwise explained, the event is deemed irreversible, the participant is lost to follow-up (as defined in Section 8.3), or for suspected cases, until SARS-CoV-2 infection is ruled-out.
 
Please refer to Section 9.2, and Appendix 3 for further details regarding the collection and follow-up of AEs.

Concomitant Medications	X (see notes)	X (see notes)	All medications with a start date within 135 days of the last dose date of study drug are considered concomitant.
Laboratory Tests			
Pregnancy Test (WOCBP)	X		
Serum or urine (minimum sensitivity equivalent units 25 IU/L or equivalent units of HCG).
 
[REDACTED]
 
[REDACTED]

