## 5.6 Clinical Pharmacology Summary

### 5.6.1 Nivolumab Clinical Pharmacology Summary

Nivolumab pharmacokinetics (PK) was assessed using a population PK approach for single agent nivolumab.

*Nivolumab as a single agent:* The PK of single-agent nivolumab was studied in patients over a dose range of 0.1 to 20 mg/kg administered as a single dose or as multiple doses of nivolumab as a 60-minute intravenous infusion every 2 or 3 weeks. Nivolumab CL decreases over time, with a mean maximal reduction (% coefficient of variation [CV%]) from baseline values of 24.5% (47.6%) resulting in a geometric mean steady-state clearance (CLss) (CV%) of 8.2 mL/h (53.9%) in patients with metastatic tumors; the decrease in CLss is not considered clinically relevant. Nivolumab clearance does not decrease over time in patients with completely resected melanoma, as the geometric mean population clearance is 24% lower in this patient population compared with patients with metastatic melanoma at steady state. The geometric mean volume of distribution at steady state (Vss) (CV%) is 6.8 L (27.3%), and geometric mean elimination half-life (t1/2) is 25 days (77.5%). Steady-state concentrations of nivolumab were reached by 12 weeks when administered at 3 mg/kg every 2 weeks, and systemic accumulation was 3.7-fold. The exposure to nivolumab increases dose proportionally over the dose range of 0.1 to 10 mg/kg administered every

2 weeks. The predicted exposure (Cavg and Cmax) of nivolumab after a 30-minute infusion is comparable to that observed with a 60-minute infusion.

*Specific Populations:* The population PK analysis suggested that the following factors had no clinically important effect on the clearance of nivolumab: age (29 to 87 years), weight (35 to 160 kg), gender, race, baseline lactate dehydrogenase (LDH), PD-L1 expression, solid tumor type, tumor size, renal impairment, and mild hepatic impairment.

*Renal Impairment:* The effect of renal impairment on the clearance of nivolumab was evaluated by a population PK analysis in patients with mild (estimated glomerular filtration rate [eGFR] 60 to 89 mL/min/1.73 m^2), moderate (eGFR 30 to 59 mL/min/1.73 m^2), or severe (eGFR 15 to 29 mL/min/1.73 m^2) renal impairment. No clinically important differences in the clearance of nivolumab were found between patients with renal impairment and patients with normal renal function.

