#### 10.4.3.1 Safety Analysis

Table 10.4.3.1-1: Safety Analysis

Safety Endpoint	Description	Timeframe
Safety		
Incidence and severity of AEs, SAEs, IMAEs, other select AEs, laboratory abnormalities, drug related AEs/SAEs, death	Incidence and severity (i.e. CTC grade) of AEs, SAEs, IMAEs, other select AEs, laboratory abnormalities, drug related AEs/SAEs, death	Up to 135 days after the last dose of study treatment
Incidence of AEs leading to discontinuation	Incidence and severity of AEs leading to discontinuation of study treatment	Up to discontinuation of study treatment

[figure not shown]
Abbreviations: AE, adverse event; CTC, Common Terminology Criteria; IMAEs, immune mediated adverse events; SAE, serious adverse event.

[figure not shown]
[REDACTED]  
[REDACTED]  
[REDACTED]

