#### 10.4.5 Other Safety Analysis

All safety analyses will be performed using the Safety analysis population.

Endpoint	Statistical Analysis Methods
The Safety and tolerability objective will be measured by the incidence and severity of adverse events (AEs), serious adverse events (SAEs), and adverse events leading to discontinuation study drug, select AEs, immune-mediated AEs (IMAEs), other events of special interest (OESIs), deaths, and laboratory abnormalities in each arm.	All safety analyses will be performed using the safety analysis population. The frequency of deaths, adverse events (AEs), serious adverse events (SAEs), AEs leading to discontinuation of study drug, select AEs, immune-mediated AEs (IMAEs), other events of special interest (OESIs), and abnormalities in specific clinical laboratory assessments will be presented. The safety summaries will be presented by severity where applicable. Analyses will be conducted using the 30-day and/or 135-day safety window from day of last dose received. AEs will be coded using the most recent Medical Dictionary for Regulatory Activities (MedDRA) version available during the conduct of the study. AEs and laboratory values will be graded for severity according to the National Cancer Institute (NCI) Common Terminology Criteria for Adverse Events (CTCAE) version 5.0.

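### Drug-related SAEs and treatment-related deaths with onset after Day 135 must be reported but fall outside the safety endpoint as defined

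*Combined protocol and SAP*

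**What the plan says.** On analysis, the entry for the safety analysis set in Section 10.3 has two sentences. The first has no time limit: "All safety events reported for all randomized participants who are exposed to study drug". The second says that, after discontinuation, "all events post-discontinuation up to Day 135 post last dose of study intervention will be included in the safety summaries". Table 10.4.3.1-1 (Section 10.4.3.1) defines the endpoint as "Incidence and severity of AEs, SAEs, IMAEs, other select AEs, laboratory abnormalities, drug related AEs/SAEs, death" and gives its timeframe as "Up to 135 days after the last dose of study treatment". Section 10.4.5 adds: "Analyses will be conducted using the 30-day and/or 135-day safety window from day of last dose received".

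On collection, Section 9.2.1 sets the routine period for SAEs at consent to 135 days after dosing stops, and for non-serious AEs at a minimum of 135 days after treatment. It then says: "The investigator must report any SAE that occurs after these time periods and that is believed to be related to study intervention". The same section requires prompt notification of any related SAE, including a death, that the investigator learns of after a participant has left the study, but it imposes no duty to look for such events. Table 2-3 says: "Beyond 135 days from the last dose of study therapy, participants will be followed for drug-related AEs/SAEs until resolution".

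**The concern.** The collection rule for serious related harm is open-ended, while the analysis rule stops at a fixed day. If the analysis rule is applied as written, related SAEs and treatment-related deaths that sites had to report do not enter the endpoint meant to describe them.

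Participants here are free of disease at entry and are treated for up to a year, so serious late toxicity is part of the benefit-risk balance. Section 3.3.3 commits the sponsor to judging risk against benefit on all available data. An endpoint that omits the late part of the reported serious related events describes that balance incompletely.

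**Working it through.** No sample size, power or alpha is involved, and the plan states no figure to reproduce. The check compares the rules and then applies them to test cases.

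1. **A related SAE with onset on Day 150 after last dose.** Section 9.2.1: must be reported. Section 10.3, second sentence: beyond Day 135, so not among the events stated to be included. Table 10.4.3.1-1: outside the timeframe. Section 10.4.5: outside both the 30-day and the 135-day window. Result: reported, but outside the endpoint.

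2. **A treatment-related death on Day 150.** The safety result is the same. The death also counts in OS, which covers death from any cause in all randomized participants without a 135-day limit (Table 4-1, Section 10.3). OS does not record whether treatment caused it.

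3. **A related SAE with onset on Day 120, resolving on Day 200.** Already inside the window. The Table 2-3 note mainly concerns this case, following events to their outcome. The duty to report new late events therefore rests on Section 9.2.1, and it covers SAEs only.

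4. **A related non-serious event with onset on Day 150.** No clear collection duty exists, since 135 days is the stated minimum and later reporting is required only for related SAEs.

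5. **Is there follow-up time after the cut-off?** Inputs: a maximum of 13 doses, one every 28 days (Section 5.1, Table 2-2). With no delays, the last dose falls on Day 1 + 12 × 28 = Day 337. The window closes on Day 337 + 135 = Day 472, which is (336 + 135)/7 = 67.3 weeks after first dose. That is 108 − 67.3 = 40.7 weeks before the Week 108 imaging point, ignoring the allowance of up to 3 days between randomization and first dose. Survival contact every 12 weeks continues as well (Table 2-3). Follow-up therefore runs well past the cut-off, and late reports are possible.

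6. **Illustration of size (assumption, not an estimate).** Section 3.2.6 reports 3 treatment-related deaths among 355 combination-treated participants in CA224047, or 3/355 = 0.85%. Applied to 525 participants (Section 5.2), this gives 525 × 3/355 = 4.4 expected. Let f be the share with onset after Day 135; the documents give no value. Expected omissions are 4.4 × f, and the chance of omitting at least one is 1 − (1 − f × 3/355)^525:

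   - f = 10%: 0.44 expected, 36% chance
   - f = 20%: 0.89 expected, 59% chance
   - f = 30%: 1.33 expected, 74% chance

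   CA224047 enrolled untreated advanced melanoma rather than resected disease, so its rate may not carry over. The calculation shows only that, with counts this small, one omitted death could matter.

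**The case against.** The strongest case for the plan is that a 135-day endpoint is sound practice. It matches the period in which all events are collected systematically in both arms. Afterwards, capture depends on the investigator judging an event related and on hearing of it at all. Participants whose disease has recurred may be on another systemic therapy, which makes attribution harder. Late deaths are not lost to the trial, because OS counts them, and the DMC reviews unblinded safety data throughout (Section 7.3). All of this stands, and it is why the window should stay for comparative incidence. It does not explain why serious related events that were reported should have no defined place in the safety results.

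It can also be said that the first sentence of the safety analysis set covers all reported events. Read alone it does. The timeframe in Table 10.4.3.1-1 and the windows in Section 10.4.5 close that reading, but the two sentences still conflict.

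A reader might infer that late events appear in no planned output. The documents do not support that. Section 10.4 describes itself as a summary and defers detail to a SAP whose text is not available here. Parts of Table 10.4.1-2 and of Section 10.4.3.1 are also redacted.

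A reader might also argue from pharmacology that Day 135 is too early, because nivolumab "geometric mean population clearance is 24% lower in this patient population compared with patients with metastatic melanoma at steady state". That does not follow. No section ties the safety window to a number of half-lives. Section 5.5.1 considers the lower clearance and does not expect it to be clinically relevant, given the flat exposure-response relationship for safety. Nivolumab is also given in both arms.

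**Conclusion.** The mismatch is real and narrow. As defined, related SAEs and treatment-related deaths with onset after Day 135 are reportable but outside the safety endpoint. What may be missing is a by-arm account of serious late harm attributed to treatment; the deaths themselves remain in OS. This holds on the visible text and assumes that neither the redacted passages nor the SAP already provides such a listing.

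The size is unknown, because the documents give no frequency of late-onset related events and any count per arm would be an assumption. A reader might infer that the omission falls more heavily on the combination arm, since CA224047 showed more Grade 3-4 drug-related events there (18.9% against 9.7%). Those are overall rates. The documents contain no late-onset data by arm, so a differential bias is not shown.

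Severity is minor: a cheap improvement to reporting, not a flaw in the comparison of arms.

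**What to change.** - Keep the 135-day window for all-causality and comparative incidence summaries.
- In Section 10.3, reconcile the two sentences of the safety analysis set so that it is clear which summaries the Day 135 limit governs.
- In Table 10.4.3.1-1, Section 10.4.5 and the SAP, add a by-arm table, in all treated participants, of drug-related SAEs (including serious drug-related IMAEs) and treatment-related deaths. Set no upper time limit, and split by onset within or after Day 135.
- State with the table that events after Day 135 depend on investigator attribution and are not actively sought in former participants.
- Do not extend the table to late non-serious IMAEs, which sites have no clear duty to report.

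The cost is a few lines of SAP wording and one additional table from reports that sites must already submit. The downside is that ascertainment after Day 135 is less systematic, so those rows should be read as descriptive. If the SAP already has such a listing, only the wording in Sections 10.3, 10.4.3.1 and 10.4.5 needs attention.
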